6.2 Safety endpoints

6.2.1 Main safety endpoints

The main secondary endpoints in this trial are, for each subject, occurrence of the following clinically meaningful safety events at up to 6 months:

- Steal
- Infection
- Aneurysm
- Seroma

These four safety endpoints have been selected since they are the major non-thrombotic access site complications associated with fistulas. Thrombotic complications which affect maturation and patency will be covered in this trial by the primary and secondary effectiveness endpoints.

These endpoints, which are defined in Section 6.4, will be scored dichotomously for each subject as 0 (did not occur) or 1 (occurred); i.e. each subject is scored 0 or 1 on each of the four endpoints. Additionally, the cumulative number of events over all subjects will be computed. This will allow both detailed and general comparisons to the relevant literature.

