 1. Mild - Cool extremity with few symptoms but demonstrable by flow augmentation with fistula occlusion), no treatment needed
 2. Moderate - Moderate (intermittent ischemia only during dialysis/ Claudication), intervention sometimes needed
 3. Severe - Severe (ischemic pain at rest/tissue loss), intervention mandatory
11. Arteriovenous fistula aneurysm – Local outflow vein dilation to at least three times the diameter of the adjacent normal vein with a minimum aneurysm diameter of 2 cm.⁴
12. Access site infection – Infection at anastomosis site graded as follows:
 1. Resolved with antibiotic treatment
 2. Loss of AV access because of ligation, removal, and possible bypass
 3. Loss of limb
13. Seroma³ – Collection of seroma fluid or hematoma at anastomosis site which requires treatment, graded as follows:
 1. Observed, resolved without treatment
 2. Aspirated, surgical treatment
 3. Loss of AV access
14. Device related SAEs or device integrity failures – any identified device failure and/or SAE which is judge by the investigator to be related to the device, as defined in section 8.2.5.

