10.2.1 Historical safety data

A search of the literature yielded two papers with data on non-thrombotic complications up to a period of 6 months. Based on these papers, SOC fistula safety can be estimated, whose rates with respect to the steal, infection, aneurysm, and seroma are presented in Table 10-1 below:

Table 10-1: Safety data from literature

Paper	Country	N	Steal (%)	Infection (%)	Aneurysm (%)	Seroma (%)	Overall rate [#]
Schinstock et al. Outcomes of Arteriovenous Fistula Creation after the Fistula First Initiative. Clin J Am Soc Nephrol 6: 1996–2002, 2011	USA	293	5.1	7.5	2.4	1.4	7.5 - 16.4
Dunlop et al. Vascular access: experience with the brachiocephalic fistula. Annals of the Royal College of Surgeons of England (1986) vol. 68	Scotland	77	6.5	2.6	3.9	NR*	6.5 – 13.0

Document title: VasQ FDA pivotal Protocol	Document No. CD0121	Revision 12.0 14 March 2021	Page 31 of 42
--	------------------------	-----------------------------------	------------------

*NR=Not reported

*Assuming no subject experienced more than one AE (which we know is not the case) the rate for experiencing any AE is the sum of the rates. Assuming every subject experienced all of the AEs (which we know is not the case) the rate experiencing any AE is the largest percentage reported

Note that:

- The study done in 1986 reports relatively similar rates to the most recent study. The SOC in this indication has changed little in 40 years so that we can expect older data to be as valid for comparison as newer.
- The Schinstock et al study was done in the Mayo Clinic in the US and included nearly 300 patients. For this reason, we propose it as the main comparison to the data to be collected in our own study.
- Importantly, AE rates are reported separately for the each of the four AEs allowing for a detailed comparison of new treatment to the SOC
- The rates reported in the above table overlap so that the average number of AEs for subjects who had these AEs is more than one. Neither of the papers provides an overall rate of subjects who experienced any of the four AEs.

Several additional papers which report data on one or more of the four complications are provided in Table 10-2 in support of the safety values to which the study observed data can be compared. Overall, it can be observed that values for all 4 events converge around single digit incidence rate for each event.

Table 10-2: Additional safety data from the literature

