10.2.2 Methodology for assessing safety

Laminate believes that the most appropriate way for assessing safety in the current study is to compare the rates for each type of AE obtained in the study with those reported in the literature. Such a multidimensional comparison will provide a more complete picture of the VasQ's safety profile than comparing an overall rate combining AEs with different clinical implications. Given the four comparisons, we feel it is most appropriate they be done descriptively. First, because statistical testing would involve 4 separate tests, along with associated issues of Type I Error and power (for success in all 4). Second, as noted, neither study provides overall, non-overlapping rates for these four non-thrombotic AEs, nor can this be obtained from the more detailed data presented in the articles (and shown in the preceding section). For this reason a statistical comparison of overall AEs rate cannot be done.

It is important to add that a descriptive comparison of each of the 4 rates between the current trial and Schinstock et al. is meaningful given that the precision of each of the (relatively small) rates is 2% to 4%; i.e. given the small AE rates involved, the planned N for our study of 116 evaluable patients will provide good precision that, in turn, will provide a meaningful comparison between our rates and those reported by Schinstock et al. In addition, even the upper bound higher rate (16.4%) has a precision of 4%. Precision is here defined as the half width of the two sided, 95% confidence interval computed using the Exact Binomial method.

Consequently, we propose evaluating safety in our trial by presenting the 4 AEs listed along with associated two-sided, 95%, Exact Binomial confidence interval to those presented in Schinstock et al. In conclusion, we feel that the most appropriate safety assessment for the VasQ is by:

- Evaluating each of the four AEs of interest separately
- Presenting safety data with two-sided 95% confidence intervals of high precision; i.e. that are relatively narrow at $\pm 3\%$ to 4%

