12 CLINICAL EVENTS COMMITTEE AND DATA SAFETY MONITORING BOARD

An independent clinical events/data safety committee will be formed to review abstracted clinical data and determine when the safety endpoints (steal, infection, aneurysm, seroma) have been met according to protocol definitions. The committee will comprise 3 physicians, who will not participate in the enrollment or treatment of subjects in this trial. In addition to the above listed safety endpoint components, all events of fistula failure and/or intervention will be reviewed by the committee and assessed for device relatedness. Any such event will trigger the accumulation of a portfolio of pertinent documents from the hospital admission. These documents will be collected and copies distributed to members of the CEC Committee. The interpretation of the event as classified and adjudicated by the clinical events committee will be used in the safety analysis.

In addition, the committee will review the progress of the trial following the enrollment of subjects and as requested on an ad hoc basis, to ensure that subject safety is not being compromised.

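### The infection endpoint counts only infection at the anastomosis, the 7.5% comparator has no stated site, and the study's infection rate may therefore be understated by an unknown amount

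*Combined protocol and SAP*

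**What the plan says.** All references are to the combined protocol and SAP.

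- **Definition.** Section 6.4 no. 12 reads "Access site infection – Infection at anastomosis site graded as follows". The grades are resolution with antibiotics, loss of the access, and loss of the limb.
- **Reason for the endpoint.** Section 6.2.1 chooses steal, infection, aneurysm and seroma because "they are the major non-thrombotic access site complications associated with fistulas".
- **Scoring.** Section 6.2.1 adds: "These endpoints, which are defined in Section 6.4, will be scored dichotomously for each subject as 0 (did not occur) or 1 (occurred").
- **Adjudication.** Under Section 12 the committee is to "determine when the safety endpoints (steal, infection, aneurysm, seroma) have been met according to protocol definitions", and its classification is the one used in the safety analysis.
- **Comparator.** Sections 10.2.2 and 10.6.5 set each rate beside the Mayo Clinic series in Table 10-1. That row reads "293 5.1 7.5 2.4 1.4 7.5 - 16.4": 293 patients, infection 7.5%. The column is headed only Infection (%).
- **Type of comparison.** Section 10.2.2: "Given the four comparisons, we feel it is most appropriate they be done descriptively". There is no test and no threshold.
- **Other capture.** Section 8.1 records other fistula-related adverse events at each on-site visit, and serious adverse events throughout. Section 8.4 says that events related to giving dialysis need not be reported.

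**The concern.** The label and the rationale speak of the access site, but the scoring rule covers one part of it. The committee is bound by that rule, and nothing in the plan lets it score an infection of the cannulation zone or the more distant outflow vein as 1. The aneurysm definition in the same list covers the outflow vein, so the anastomosis limit is not common to all four endpoints.

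The edge of the definition is also unclear for the implant itself. Section 2.2 describes a braided part around the vein welded to a tube around the anastomosis, and Section 7.3 uses a 6 cm incision. The plan does not say whether infection of the incision, or along the braided part, is at the anastomosis site.

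With no test or threshold, the displayed rates and intervals carry the safety conclusion. They can be read against each other only if both sides count the same kind of event. If the comparator counted infection anywhere on the access, part of any favourable difference would come from the definition.

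**Working it through.** **1. The plan's own precision figure.** Section 10.2.2 says that "the planned N for our study of 116 evaluable patients will provide good precision", put at 2% to 4% per rate. It adds: "Precision is here defined as the half width of the two sided, 95% confidence interval computed using the Exact Binomial method". The exact limits for x events in n are:

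- lower = 2.5% quantile of Beta(x, n − x + 1)
- upper = 97.5% quantile of Beta(x + 1, n − x)

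At n = 116, with x set to the comparator rate times 116, the half-widths are 2.7, 3.3, 4.5 and 5.2 points for rates of 1.4, 2.4, 5.1 and 7.5%. The stated range is not reproduced for infection. At n = 293 the half-widths are 1.5, 1.9, 2.7 and 3.2, closer to what is stated. That is a separate matter. It is noted here because the infection interval is wider than the plan implies, and the recalculated intervals are used below.

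**2. The comparator.** 0.075 × 293 = 21.98, so about 22 patients. The exact 95% interval for 22/293 is 4.8% to 11.1%.

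**3. Direction.** Every infection at the anastomosis is also an infection of the access. So, for the same patients, scored rate ≤ any-site rate, with equality only if no patient has an infection solely away from the anastomosis.

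**4. Size, by assumption.** Let s be the share of infected patients whose infection lies only away from the anastomosis. The documents do not give s. Take an any-site rate of 7.5%. Then scored rate = 7.5% × (1 − s). Counts are rounded to whole events in 116.

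| s | Expected scored rate | Events in 116 | Observed rate | Exact 95% interval |
|---|---|---|---|---|
| 0 | 7.5% | 9 | 7.8% | 3.6% to 14.2% |
| 10% | 6.75% | 8 | 6.9% | 3.0% to 13.1% |
| 25% | 5.6% | 7 | 6.0% | 2.5% to 12.0% |
| 50% | 3.75% | 4 | 3.4% | 0.9% to 8.6% |
| 75% | 1.9% | 2 | 1.7% | 0.2% to 6.1% |

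Up to s = 50% the interval still contains 7.5%. At 75% it does not, although it still overlaps the comparator's own interval.

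**5. The reverse reading.** If the study scored 7.5%, the any-site rate would be 7.5% / (1 − s): 8.3%, 10%, 15% and 30% for s = 10, 25, 50 and 75%.

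**6. Other denominators.** The safety set in Section 10.5.1 is all implanted subjects, so 129 (main cohort) or 144 (both cohorts) may apply. At s = 50% these give 5/129 = 3.9% (1.3% to 8.8%) and 5/144 = 3.5% (1.1% to 7.9%). The picture does not change.

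**7. Is the event caught elsewhere?** Section 8.1 would record an off-anastomosis infection as another fistula-related adverse event. Section 8.4 can be read as exempting a needle-site infection, because it arises from giving dialysis. On that reading a non-serious one could be missing from the adverse event tables as well as from the endpoint.

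**The case against.** A reader might infer that the study's infection rate is too low against 7.5%. The documents do not support that. It would require the comparator series to have counted infection at any site, and a bare column heading is not evidence of a broad definition. If that series used the same narrow site, there is no bias.

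A reader might also infer that infections which cost the patient the access drop out of the safety record. They do not. Serious events are followed to 24 months, and Section 12 has the committee review every fistula failure or intervention. A fistula lost before 180 days that meets none of the three patency conditions fails the primary endpoint, and abandonment ends secondary patency. Such an event can be absent from the infection tally, but not from the trial's data.

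A local definition can also be defended. Seroma carries the same anastomosis limit, and the implant sits at the anastomosis and the adjacent vein. Widening the count without knowing how the comparator counted could create the opposite mismatch.

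All of this stands, and it limits the claim. It does not answer two points: the plan does not show that the two rates are comparable, and any distortion within the study can go only one way. A deliberately narrow endpoint would still need a comparator shown to be equally narrow.

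**Conclusion.** The point holds as a question of comparability. As written, infection elsewhere on the study fistula scores 0 on an endpoint labelled and justified as an access-site complication. It is then compared with a figure whose site definition is not given. The study's infection rate may be understated relative to that figure. The amount ranges from nothing (s = 0) to a halving (s = 50%) or more, and the documents do not allow a choice within that range. The table rests on two assumptions: an any-site rate of 7.5% and the listed values of s.

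At the planned size, a shift of up to half would stay within the exact interval, so it would move the displayed point estimate more than any formal conclusion. The consequence is confined to a descriptive safety comparison. The effectiveness test and its success rule are untouched.

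The grades have a small gap: an infection treated surgically with the access preserved fits none of the three. If it lies at the anastomosis it still meets the definition and scores 1, so only the grade table in Section 10.6.5 is affected.

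**What to change.** - **Sections 6.4 no. 12 and 10.6.5.** Have the committee adjudicate any infection of the study access (incision, anastomosis, outflow vein, cannulation zone). Report that rate with its exact 95% interval, and report anastomosis-site infection as a subset, also with its interval.
- **Sections 10.2.1 and 10.6.5.** Set both rates beside the 7.5%, and state how the comparator series defined and located infection. If the source does not say, state that. Showing both rates protects the comparison whichever definition the comparator used.
- **Section 8.4.** State that the exemption for events related to the administration of dialysis does not remove infections of the study access from this count.
- **Grades (minor).** Add a category for infection treated surgically with the access preserved.

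**Cost.** This is definition and committee text plus one extra table row. A small number of events already recorded may need adjudication. Needle-site infections left unreported under Section 8.4 may have to be sought in site and dialysis records. The reported infection rate may be higher.

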10.6.5 Safety analyses

Safety analyses will be conducted on the safety analysis set. The main safety analyses will compare descriptively between AE rates for Steal, Infection, Aneurysm and Seroma as described in section 10.2.2. That is, we will present point estimates along with Exact Binomial, two-sided, 95% confidence intervals for each of these events separately for both our study and Schinstock et al.

Additionally, descriptive statistics will be provided, with SAE's and AE's coded by body system, preferred term, arm, severity, relation to procedure by arm and outcome. Rate of freedom from major device-related adverse events will be provided along with associated two-sided 95% Exact Binomial confidence intervals.

In addition to the dichotomously scored endpoints we will also present frequency and percent for grade for steal (mild; moderate; severe), infection (resolved with antibiotic; loss of AV; loss of limb) and seroma (resolved without treatment; aspirated, surgical treatment; loss of AV access).

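### The seroma endpoint counts treated hematomas, but its 1.4% comparator is labelled seroma with no definition, so the two rates may not count the same events

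*Combined protocol and SAP*

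**What the plan says.** Seroma is one of the four main safety endpoints, each scored 0 or 1 per subject up to 6 months (section 6.2.1). Section 6.4 no. 13 defines it as "Collection of seroma fluid or hematoma at anastomosis site which requires treatment". Grade 1 of the same item reads "Observed, resolved without treatment".

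Section 10.2.1 takes standard-of-care safety from two papers, "whose rates with respect to the steal, infection, aneurysm, and seroma are presented in Table 10-1 below". The column headings are "Steal (%) Infection (%) Aneurysm (%) Seroma", and the row for the Mayo Clinic study, the main comparator, reads "USA 293 5.1 7.5 2.4 1.4". Neither the table nor its notes say how that study defined seroma, whether hematomas were counted, or whether a collection had to be treated.

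Section 10.2.2 explains the type of comparison: "Given the four comparisons, we feel it is most appropriate they be done descriptively". It adds that "the planned N for our study of 116 evaluable patients will provide good precision". Under section 10.6.5, "we will present point estimates along with Exact Binomial, two-sided, 95% confidence intervals for each of these events separately", for this trial and for the Mayo Clinic study. Seroma is then broken down by grade only.

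**The concern.** A side-by-side comparison without a test or limit is only as good as the match between the two definitions. Here the trial's numerator includes hematoma in express words, the comparator carries a one-word label, and nothing in sections 10.2 or 10.6.5 aligns them. Section 10.2.2 itself argues against merging events whose clinical meaning differs, yet this endpoint merges two.

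At stake is how one of the four main safety results is read. A raised rate could be post-operative hematoma and not a serous collection around the implant. Equally, a real excess of serous collections could be put down to hematoma. The planned seroma lines, total and by grade, could not settle which. Seroma also has the lowest of the four comparator rates, so it is the one most easily moved by a handful of events.

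**Working it through.** **Inputs from the documents.** Comparator rate 1.4%, N = 293 (Table 10-1). Planned evaluable N = 116 (10.2.2). Main cohort N = 129, all implanted and so all in the safety set (5.1, 7.2, 10.5.1). Intervals are two-sided 95% exact binomial; precision is the half width (10.2.2).

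**Assumption.** The rate *h* of treated hematoma is not in the documents. It is varied from 0% to 5%.

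**1. The plan's own figure.** Section 10.2.2 states a precision of 2% to 4%. At N = 116 and 1.4% the expected count is 0.014 × 116 = 1.62, giving a half width of 2.7%. With the whole count 2/116 the interval is 0.2% to 6.1%, half width 2.9%. The stated precision reproduces for seroma.

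**2. The comparator.** 0.014 × 293 = 4.1, so about 4 events; 4/293 has an exact interval of 0.4% to 3.5%.

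**3. Matched definitions, no device effect.** Expected count in 129: 0.014 × 129 = 1.8. Two events give 2/129 = 1.6% (0.2% to 5.5%), ratio to 1.4% about 1.1.

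**4. Comparator excludes hematomas, trial counts them.** Expected ratio = (1.4% + *h*) / 1.4%; expected count = (0.014 + *h*) × 129. The last column is the binomial probability of 6 or more events in 129, the smallest count at which the observed rate is at least three times 1.4%. It is also the smallest count whose lower exact limit exceeds 1.4%.

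| *h* (assumed) | Expected events in 129 | Ratio to 1.4% | P(6 or more of 129) |
|---|---|---|---|
| 0% | 1.8 | 1.0 | 1% |
| 1% | 3.1 | 1.7 | 9% |
| 2% | 4.4 | 2.4 | 28% |
| 3% | 5.7 | 3.1 | 50% |
| 4% | 7.0 | 3.9 | 70% |
| 5% | 8.3 | 4.6 | 84% |

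In counts: 2 serous collections plus 4 treated hematomas give 6/129 = 4.7% (1.7% to 9.8%), ratio 3.3. At N = 116, 2 plus 3 give 5/116 = 4.3% (1.4% to 9.8%), ratio 3.1.

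**5. The opposite mismatch.** Suppose the comparator counted untreated collections as well, and only a fraction *f* of its events was treated (also not in the documents). With no hematomas in the trial, the expected ratio is (1.4% × *f*) / 1.4% = *f*. For example, *f* = 0.5 gives 0.7%, or 0.9 expected events in 129, half the comparator with no device effect.

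**6. Internal consistency of no. 13.** The definition requires treatment; grade 1 is a collection that resolved without it. Read literally, grade 1 can never score 1, yet it is listed as a grade of the endpoint and 10.6.5 tabulates it. For steal (no. 10) the protocol says which grades count; for seroma it does not.

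**The case against.** A reader might infer that the 1.4% is a rate for seroma alone and that the endpoint will make the device look several times worse. The documents support neither step. The only evidence on the comparator is a column heading, and the protocol uses the same single word for its own endpoint, which includes hematoma. The label therefore cannot show that hematomas were left out. The multiples rest on an assumed hematoma rate: at 1% the ratio is below two, and roughly 3% is needed for a threefold excess. Even 6/129 (1.7% to 9.8%) overlaps 4/293 (0.4% to 3.5%), and Table 10-2 reports seroma rates of up to 4.2%.

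Further points also stand. Section 8.5 names hematoma and seroma as separate terms but within one list item, so it does not clearly treat them as distinct. Adverse events are coded by preferred term and listed by subject (10.6.1, 10.6.5), so treated hematomas could partly be recovered. Definition 13 cites a published reporting standard and is not ad hoc. No success criterion depends on the rate.

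These arguments limit the size of the point but do not remove it. Preferred-term tables are not tied to the adjudicated endpoint, carry no planned exact interval and are not set beside 1.4%. A reporting standard behind the trial's definition does not show that the comparator used it. That the comparison is descriptive makes matching definitions more important, since nothing else supports the inference.

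**Conclusion.** The point holds as a question of comparability. The trial endpoint expressly includes treated hematoma, the comparator's definition is not stated, and the planned tables neither align nor separate the two. If the comparator excludes hematomas, the expected ratio with no device effect is 1.0 to 4.6 for an assumed added rate of 0% to 5%. If it includes untreated collections, the treatment requirement pulls the ratio below 1. Both mismatches could be present, so the net direction is unknown and no bias for or against the device is established. The primary effectiveness analysis is untouched. Separately, and without any outside source, no. 13 contradicts itself on whether an untreated collection belongs to the endpoint.

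**What to change.** - **10.6.5:** keep the combined rate as defined, and add separate serous and hematoma rates, each with an exact 95% interval. The clinical events committee already reviews each case against the protocol definitions (section 12) and can record the type of collection.
- **10.2.1:** state how the Mayo Clinic study defined seroma, including hematoma and any treatment requirement, or state that this is unknown. Set beside 1.4% the line that matches; if unknown, show the combined and the serous lines together. Showing only the serous line could itself be an unlike comparison that favours the device, if the 1.4% includes hematomas.
- **6.4 no. 13:** reconcile the treatment requirement with grade 1, so that it is clear which grades score 1.

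The cost is a few sentences, one classification field for cases already under review, and extra table rows. There are no new visits or subjects. The drawback is a smaller count in each separate line, and so less information per line.
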